### 8.1 Definitions

An **AE** is any untoward medical occurrence associated with the use of a drug in humans, whether or not considered drug-related. An AE (also referred to as an adverse experience) can be any unfavorable and unintended sign (eg, an abnormal laboratory finding), symptom, or disease temporally associated with the use of a drug, without any judgment about causality. An AE can arise from any use of the drug (eg, off-label use, use in combination with another drug) and from any route of administration, formulation, or dose, including an overdose. Overdose includes only clinically symptomatic doses that are at least twice the intended dose.

An abnormal laboratory value will not be assessed as an AE unless that value leads to discontinuation or delay in treatment, dose modification, therapeutic intervention, or is considered by the Investigator to be clinically significant.

In general, disease progression should not be reported as an AE (or an SAE), or cause of death in this Study. Instead the AEs (or SAEs) considered as complications of disease progression should be reported. However, if no specific complications of disease progression can be identified that explain the clinical observations, “disease progression” may be reported as an AE, SAE, or cause of death

## 9 SERIOUS ADVERSE EVENTS

### 9.1 Definition of Serious Adverse Event

A SAE is any event that meets any of the following criteria:

- Death
- Life-threatening

A serious adverse event is life threatening if the patient was at immediate risk of death from the event as it occurred; i.e., it does not include a reaction that if it had occurred in a more serious form might have caused death. For example, drug-induced hepatitis that resolved without evidence of hepatic failure would not be considered life threatening even though drug induced hepatitis can be fatal.

- Inpatient hospitalization or prolongation of existing hospitalization

Adverse events requiring hospitalization should be considered SAEs. Hospitalization for elective surgery or routine clinical procedures that are not the result of AE (e.g., elective surgery for a pre-existing condition that has not worsened) need not be considered AEs or SAEs. If anything, untoward is reported during the procedure, that occurrence must be reported as an AE, either 'serious' or 'non-serious' according to the usual criteria.

In general, hospitalization signifies that the patient has been detained (usually involving at least an overnight stay) at the hospital or emergency ward for observation and/or treatment that would not have been appropriate in the physician's office or outpatient setting. When in doubt as to whether 'hospitalization' occurred or was necessary, the AE should be considered serious.

- Persistent or significant disability/incapacity

An SAE is incapacitating or disabling if the experience results in a substantial and/or permanent disruption of the patient's ability to carry out normal life functions.

- Congenital anomaly/birth defect in the offspring of a subject who received avapritinib.
- Other: Important medical events that may not result in death, be life-threatening, or require hospitalization, may be considered an SAE when, based upon appropriate medical judgment, they may jeopardize the subject and may require medical or surgical intervention to prevent one of the outcomes listed in this definition.

Examples of such events are:

- Intensive treatment in an emergency room or at home for allergic bronchospasm ○
- Blood abnormalities or convulsions that do not result in inpatient hospitalization ○
- Development of drug dependency or drug abuse

## 9.2 Reporting Serious Adverse Events

All SAEs or serious pretreatment events must be reported by the Investigator to the Sponsor or its designee within 24 hours from the point in time when the Investigator becomes aware of the SAE. In parallel, SAEs will be captured in the safety database only, they will not be captured in an CRF. The same 24-hour timeline applies for any follow-up information received by the Investigator.

**NOTE: Compliance with this time requirement is essential so that the Sponsor may comply with its regulatory obligations.**

- All SAEs must be reported whether or not they are considered causally related to study treatment.
- SAE forms will be completed in English language and should contain, at a minimum:
  - Patient number/ID, sex, and age/year of birth
  - The date of the report
  - Name of the Investigator
  - Name of the suspected study drug
  - Assessment of event severity/intensity (and/or NCI CTCAE Grade)
  - Investigator causality assessment
  - A description of the event, including event term(s), seriousness criteria, and a clinical summary of the event
  - SAEs with outcome ‘death’: cause of death, autopsy or death certificate, as applicable and available

Refer to the study manual for reporting instructions.

### **9.3 Documenting Serious Adverse Events and Adverse Events of Special Interest**

Each patient must be carefully monitored for the development of any SAEs and AESIs, Adverse Events of Special Interest for avapritinib are, regardless of grade or causality:

- cognitive effects which include the following terms: memory impairment, cognitive disorder, confusional state and encephalopathy.
- intracranial bleeding including haemorrhage intracranial, cerebral haemorrhage, and subdural haematoma.

This information should be obtained in the form of non-leading questions (eg, “How are you feeling?”) and from signs and symptoms detected during each examination, observations of study personnel, and spontaneous reports from patients.

All SAEs and AESIs reported by the patient or revealed by observation, physical examination, laboratory testing or other diagnostic procedures will be recorded in the appropriate section of the CRF. When possible, signs and symptoms indicating a common underlying pathology should be noted as one comprehensive event.

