#### **4.4 Exclusion Criteria**

Patients meeting any of the following criteria will not be eligible for Study participation:

1. Patient requires therapy with a concomitant medication that is a strong inhibitor or strong inducer of cytochrome P450 (CYP) 3A4 (see [Section 5.4.1](#)).
2. Patient has a history of intracranial bleeding either prior to or during avapritinib treatment
3. Patients who have poor organ function, defined as Adverse Events of NCI CTCAE version 5.0 Grade 3 or higher at the time of enrollment must delay start of treatment until symptoms return to Grade 2 or baseline, or the start of treatment has been approved by the Sponsor.
4. Patients who have ongoing cognitive or mood effects Adverse Events of NCI CTCAE version 5.0 higher than Grade 1 must delay start of treatment until symptoms return to Grade 1 or baseline.
5. Women who are unwilling, if not postmenopausal or surgically sterile, to abstain from sexual intercourse or employ highly effective contraception from the time of enrollment and for at least 30 days after the last dose of avapritinib. Men who are unwilling, if not surgically sterile, to abstain from sexual intercourse or employ highly effective contraception from the time of first dose and for at least 90 days after the last dose of avapritinib. Refer to [Section 5.5.1](#) for acceptable methods of contraception.
6. Women who are pregnant, as documented by a serum beta human chorionic gonadotropin ( $\beta$ -hCG) pregnancy test consistent with pregnancy, obtained within 7 days before the enrollment. Females with  $\beta$ -hCG values that are within the range for pregnancy but are not pregnant (false-positives) may be enrolled with written consent of the Sponsor, after pregnancy has been ruled out. Females of non-childbearing potential (postmenopausal for more than 1 year; bilateral tubal ligation; bilateral oophorectomy; hysterectomy) do not require a serum  $\beta$ -hCG test.
7. Women who are breast feeding.
8. Patients with a known hypersensitivity to avapritinib or the excipients.

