**Table 2: Dose Modification Guidelines for Avapritinib-related Toxicity**

Toxicity	Modification
General	
Grade 1 or Grade 2	
 
• No dose modification required
 

Grade 3 - 4	
 
• Occurrence: Hold until event is <math>\leq</math> Grade 2, or has returned to baseline, and then resume by reducing the dose by 100 mg less than the current dose 
 
◦
 
 
 
• Occurrence at 100 mg: Discontinue avapritinib 
 
◦
 
 
 

Cognitive or Mood Effects	
Grade 1 with only minor impairment	No dose modification required
Grade 1, other than minor impairment	
 
• Interrupt dosing for 7 days, and resume dosing without dose reduction
 
• The dosing interruption may be repeated if the impairment continues to worsen after resuming dosing; however, repeated dosing interruption is at the discretion of the investigator, and should be balanced with the need to treat the underlying GIST
 

Grade 2	
 
• Interrupt dosing for a minimum of 7 days
 
• Resume dosing with a dose reduction of 100 mg when the cognitive effect has improved to Grade 1 or less, or still at Grade 2, if continued treatment is considered in the best medical interest of the patient due to the underlying GIST
 
• If the patient is already receiving a dose of 100 mg QD, and continued treatment is considered in the best medical interest of the patient due to the underlying GIST, treatment may be resumed at 100 mg
 

Grade 3-4	
 
• Interrupt dosing for a minimum of 14 days
 
• Resume dosing with a dose reduction of 100 mg when the cognitive effect has improved to Grade 1 or less, or when it has improved to Grade 2, if continued treatment is considered in the best medical interest of the patient due to the underlying GIST
 
• Occurrence at 100 mg: Discontinue avapritinib
 

Intracranial Bleeding	
Grade 1-4	
 
• Discontinue avapritinib
 

Abbreviations: CNS = central nervous system; GIST = gastrointestinal stromal tumor; QD = once daily.

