 Changes in cognition, memory, attention, mood, or speech (thought to originate in the CNS). If avapritinib treatment is resumed after interruption for a cognitive or mood effect, or for an intracranial bleeding event, the investigator must document in writing that resuming avapritinib treatment was considered to be in the best medical interest of the patient.

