### **6.2.5 Adverse Events and Concomitant Medications**

Each patient must be carefully monitored for the development of any AEs throughout the study from the start of avapritinib administration (or from the time of signing informed consent, for SAEs) to 30 days after the last administration. In addition, SAEs that are assessed to be at least possibly related to Study treatment that occur > 30 days posttreatment are to be reported.

Adverse events will be recorded locally, but only SAEs will be reported to the sponsor or its designee. Complete details on AE and SAE monitoring are provided in [Section 8](#) and [Section 9](#), respectively.

Concomitant medications will be recorded from the time of signing informed consent to 30 days after the last dose.

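### The four terms named for the cognitive AESI omit isolated mood and speech changes that Table 2 puts in the same toxicity category, so non-serious events that change dosing can be missing from every planned summary

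*Combined protocol and SAP*

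**What the plan says.** Section 2 makes characterising the rate of SAEs and AESIs one of the study's two objectives. Section 9.3 names two AESIs, opening with "Adverse Events of Special Interest for avapritinib are, regardless of grade or causality". One is intracranial bleeding; the other is "cognitive effects which include the following terms: memory impairment, cognitive disorder, confusional state and encephalopathy".

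Table 2 (Section 5.3.1) singles out the same two areas for dose modification, but calls the first Cognitive or Mood Effects. Footnote 1 defines that category as "Changes in cognition, memory, attention, mood, or speech (thought to originate in the CNS"). Within it, Grade 1 with more than minor impairment leads to "Interrupt dosing for 7 days, and resume dosing without dose reduction". At Grade 2 and at Grade 3-4 dosing is interrupted, with the instruction "Resume dosing with a dose reduction of 100 mg when the cognitive effect has improved to Grade 1 or less" among the conditions for restarting.

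Mood is looked for elsewhere too. Table 1, footnote c, includes it in the screening examination and in later ones. Exclusion criterion 4 groups the two effects: "Patients who have ongoing cognitive or mood effects Adverse Events of NCI CTCAE version 5.0 higher than Grade 1 must delay start".

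On data collection, Section 8 sends serious AEs and AESIs to the CRF. Section 10 plans summaries of SAEs and AESIs by MedDRA system organ class and preferred term, of treatment duration, and of reasons for stopping treatment. The Protocol Summary adds the proportion of patients with SAEs and AESIs.

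**The concern.** The protocol examines patients for mood, attention and speech effects and modifies dosing for them, yet names none of them in the AESI that it counts. If such an event is not serious and not an AESI, nothing in Section 8 requires it in the CRF. A patient could then have dosing interrupted or reduced for a CNS effect and be shown as having had no cognitive AESI.

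At stake is how completely the study describes a toxicity that it treats as special, when long-term safety data are its only purpose. The consequence is not confined to this study: Section 10 treats these data as continuing the same patients' data from the earlier avapritinib studies, so the gap would carry into those combined safety assessments.

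**Working it through.** The plan gives no expected AESI rate, power or precision figure to reproduce. Section 10 says the sample size is an estimate of how many patients might roll over. The check is therefore mainly textual.

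**Step 1: set the two definitions side by side.**

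| Domain in Table 2, footnote 1 | Nearest term in Section 9.3 | Result |
|---|---|---|
| Cognition | Cognitive disorder; confusional state; encephalopathy | Covered |
| Memory | Memory impairment | Covered |
| Attention | None named; may fall under the general words for cognitive effects | Arguable |
| Mood | None | Gap |
| Speech | None | Gap, unless part of a confusional state or encephalopathy |

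**Step 2: follow an on-treatment mood or speech event that stands alone.**

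- If it is serious, it reaches the sponsor as an SAE (Section 9.2).
- If it ends treatment, the reason for stopping is recorded in the CRF (Section 4.6) and reported (Section 10).
- If it is part of a wider confusional or encephalopathic picture, Section 9.3 asks for one comprehensive event, which would be an AESI.
- If it is non-serious, isolated, and leads only to an interruption or reduction, none of these routes applies. Section 8 does not require it in the CRF. Section 10 has no summary of interruptions or reductions that would show it indirectly. The drug accountability records of Section 7.2 list dates, quantities and batches, not reasons.

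The last route is a realistic one, because Table 2 acts from Grade 1 upward and many Grade 1 or 2 events will not meet a seriousness criterion.

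**Step 3: what one such patient does to the proportion.** Section 4.1 gives N of about 5, so one patient is 1/5 = 20 percentage points (1/4 = 25 if four enrol, 1/6 = 17 if six do).

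**Step 4: precision, for context.** Exact 95% intervals are 0.5% to 72% for 1 of 5 patients, and 5% to 85% for 2 of 5. The 20-point step is large in absolute terms but well inside the sampling uncertainty. The loss is mainly one of individual safety information, and not a shift in a precisely estimated rate.

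**The case against.** The strongest reply is that the two lists do different jobs. Table 2 guides management of avapritinib-related toxicity; Section 9.3 selects what a deliberately light study collects, and Section 6.5 says that data will be limited. Table 2 also acts on every other Grade 3-4 toxicity, and nobody expects all of those to be AESIs. This stands to the extent that a narrower AESI is a legitimate choice. It does not remove the gap, because Table 2 and Section 9.3 single out the same two toxicities and the protocol never says that one of the pair is meant to be narrower.

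Several stronger readings are tempting, and the documents do not support them.

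- *That the AESI rate is biased.* It is a valid rate for the four terms; it measures a narrower quantity than the Table 2 category.
- *That three of the five domains are left out.* Section 9.3 introduces its terms as included examples, and cognitive disorder is broad, so attention may well be covered. The firm gap is isolated mood and speech change.
- *That these events can never reach the sponsor.* Serious events and those ending treatment do. Sections 6.5, 11.4 and 11.5 also contain general statements about reporting AEs or entering data that sit uneasily with the narrower rule in Section 8.
- *That Section 6.2.5 proves the loss.* Its sentence, "Adverse events will be recorded locally, but only SAEs will be reported to the sponsor or its designee", would, taken literally, withhold the non-serious four-term AESIs as well. That is a separate inconsistency with Sections 8 and 9.3 and says nothing about the term list.
- *That exclusion criterion 4 shows missed events.* It concerns events already present before dosing in this study. It shows that the protocol thinks of cognition and mood together, but not that on-treatment events go uncounted.
- *That the number of missed patients can be estimated from the 30% in Section 1.1.5.* One could compute 0.30 x 5 = 1.5 patients, assume that 10% to 40% of them fall outside the four terms, and get 0.15 to 0.6 missed. But the 30% is an aggregate whose terms are not listed. If it holds only terms like those in Section 9.3, the missed share of it is zero and any mood or speech patients come on top. It also comes from the earlier study, not from patients selected for continuing benefit.

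**Conclusion.** The concern holds in a limited form. Isolated mood and speech changes belong to the category on which Table 2 acts but are not among the terms named for the AESI. When such an event is non-serious and leads only to an interruption or reduction, it need not be in the CRF and appears in no planned summary. The four-term proportion then understates the CNS toxicity that the protocol manages.

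How often this will happen cannot be derived from the documents. All that can be stated is the step: 20 percentage points per affected patient if 5 enrol. The conclusion assumes that Section 8, the specific recording rule, governs over the general statements in Sections 6.5, 11.4 and 11.5, and that sites read mood and speech as outside cognitive effects. If some sites read the list more widely, omission gives way to inconsistency between sites, since no rule says which further terms count.

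With about 5 patients and purely descriptive summaries, no inference turns on this. It merits correction because it is cheap and concerns the data that the study exists to collect.

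**What to change.** Keep the four-term AESI line as it is, for continuity with the parent studies. In Section 9.3, add that every on-treatment event the investigator manages under the Table 2 Cognitive or Mood Effects category is entered in the CRF whatever its seriousness, with term, grade, start and stop dates and any dose action, and is coded to a MedDRA preferred term. In Section 10, report the proportion of patients with any such event as a second line beside the four-term AESI.

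State in Section 9.3 that the AESI set and the Table 2 category differ, or reconcile them. The second line need not contain the first: Table 2 concerns avapritinib-related toxicity, while AESIs count regardless of causality. A footnote to the table should say so.

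The cost is a wording change in two sections and a few more CRF entries in about 5 patients. The reported proportion with CNS events may be higher. No dosing rule changes.

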### **9.4 Assessment of Intensity**

Intensity of all AEs, including clinically significant treatment-emergent laboratory abnormalities, will be graded according to the National Cancer Institute (NCI) Common Terminology Criteria for Adverse Events (CTCAE), version 5.0. Adverse events not listed in the CTCAE will be graded as follows:

- Grade 1: Mild, the event is noticeable to the patient but does not interfere with routine activity.
- Grade 2: Moderate, the event interferes with routine activity but responds to symptomatic therapy or rest.
- Grade 3: Severe, the event significantly limits the patient's ability to perform routine activities despite symptomatic therapy.
- Grade 4: Life-threatening, an event in which the patient was at risk of death at the time of the event.
- Grade 5: Fatal, an event that results in the death of the patient.

## **9.5 Assessment of Causality**

Relationship to avapritinib administration will be determined by the Investigator according to the following criteria:

- Not Related: Exposure to avapritinib did not occur, or the occurrence of the AE is not reasonably related in time, or the AE is clearly caused by something other than avapritinib.
- Related: The AE does not meet the criteria for “Not Related”.

## **9.6 Pregnancy Reporting**

Pregnancy is neither an AE nor an SAE, unless a complication relating to the pregnancy occurs (eg, spontaneous abortion, which may qualify as an SAE).

Pregnancies and suspected pregnancies (including a positive pregnancy test regardless of age or disease state) of a female patient or partner of a male patient occurring while the patient is being treated with avapritinib, or within 30 days of the patient's last dose of avapritinib, are considered immediately reportable events. If a female partner of a male patient taking investigational product becomes pregnant, the male patient taking avapritinib should notify the Investigator, and the pregnant female partner should be advised to call her healthcare provider immediately. In pregnant female patients, avapritinib is to be discontinued immediately and the patient instructed to return any unused avapritinib to the Investigator. The pregnancy, suspected pregnancy, or positive pregnancy test must be reported immediately using the Pregnancy Report Form. The Investigator must follow up and document the course and outcome of all pregnancies even if the patient was discontinued from the Study or if the Study has finished. The female patient or partner of a male patient should receive any necessary counseling regarding the risks of continuing the pregnancy and the possible effects on the fetus. Monitoring should continue until conclusion of the pregnancy.

All outcomes of pregnancy must be reported by the Investigator to the Sponsor or Medical Monitor on a Pregnancy Outcome Report form within 30 days after he/she has gained knowledge of the delivery or elective abortion.

Any SAE that occurs during pregnancy must be recorded on the SAE report form (eg, maternal serious complications, spontaneous or therapeutic abortion, ectopic pregnancy, stillbirth, neonatal death, congenital anomaly, or birth defect) and reported within 24 hours in accordance with the procedure for reporting SAEs.

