#### **5.5.1     *Contraception Requirements***

Women of childbearing potential must agree to use a highly effective method of contraception ([CTFG, 2014](#)) from the time of enrollment until at least 30 days after the last dose of avapritinib. Women are considered to be of childbearing potential after

menarche until becoming postmenopausal (defined as no menses for at least 12 months without an alternative medical cause) unless permanently sterile. A high follicle stimulating hormone level in the postmenopausal range may be used to confirm a postmenopausal state in women not using hormonal contraception or hormonal replacement therapy. However, in the absence of 12 months of amenorrhea, a single follicle stimulating hormone measurement is insufficient. Permanent sterilization methods include hysterectomy, bilateral salpingectomy and bilateral oophorectomy ([CTFG, 2014](#)). Because avapritinib and regorafenib are potential CYP3A4 inducers, women should use hormonal contraception with caution and supplement with other highly effective methods.

Males with partners who are female of reproductive potential must agree that they will use condoms, and their partners will use a highly effective contraceptive method throughout their participation in the Study, and for 90 days after the last dose of avapritinib. Highly effective forms of contraception are defined as the following ([CTFG, 2014](#)):

- Combined (estrogen and progestogen containing) hormonal contraceptives that inhibit ovulation, including oral, intravaginal and transdermal products;
- Progestogen-only hormonal contraceptives that inhibit ovulation, including oral, injectable, and implantable products;
- Intrauterine devices (IUD) and intrauterine hormone-releasing system (IUS);
- Bilateral tubal occlusion (women);
- Male partner vasectomy or other method of surgical sterilization provided that the partner is the sole sexual partner of the trial participant and the vasectomized partner has received medical assessment of the surgical success;
- Sexual abstinence (men and women), when this is the preferred and usual lifestyle of the patient. Periodic abstinence (such as calendar, symptothermal and postovulation methods), withdrawal (coitus interruptus), and the lactational amenorrhea method are not acceptable methods of contraception.

The following methods of contraception are not considered highly effective ([CTFG, 2014](#)):

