### **5.5.2 Gamete and Embryo Banking**

Hypospermatogenesis was observed in the testis and epididymis of rats and dogs and did not recover after 2-week recovery. Patients should be reminded of the possibility of gamete and embryo banking.

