## 8 ADVERSE EVENTS

All patients will be monitored for adverse events throughout their participation in the Study. Serious AEs and adverse events of special interest (AESIs) will be recorded in the CRF from the time of first dose of avapritinib through 30 days after the last avapritinib dose. In addition, serious adverse events (SAEs) and AESIs that are assessed as related to avapritinib treatment and that occur > 30 days posttreatment will also be reported. All related SAEs and AESIs should be monitored until they are resolved, stabilized, have returned to pre-exposure baseline, determined to be due to another illness, or until a subsequent therapy is initiated.

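### Section 9.6 gives no reporting trigger for an uncomplicated partner pregnancy in days 31–90 after the last dose, although male contraception is required to day 90

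*Combined protocol and SAP*

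**What the plan says.** Section 9.6 (Pregnancy Reporting) covers pregnancies and suspected pregnancies "of a female patient or partner of a male patient occurring while the patient is being treated with avapritinib", and closes the window with "or within 30 days of the patient's last dose of avapritinib, are considered immediately reportable events". The same 30 days serve both groups.

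The contraception rules differ by sex. Under Section 5.5.1, women of childbearing potential must use contraception "from the time of enrollment until at least 30 days after the last dose of avapritinib". Men with female partners of reproductive potential must use condoms, with a highly effective method used by the partner, "throughout their participation in the Study, and for 90 days after the last dose of avapritinib". Exclusion criterion 5 in Section 4.4 gives the same male period: "from the time of first dose and for at least 90 days after the last dose of avapritinib".

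Three other provisions bear on late events. Section 8 adds that SAEs and AESIs "assessed as related to avapritinib treatment and that occur > 30 days posttreatment will also be reported", and Section 6.2.5 says much the same for SAEs judged at least possibly related. Section 9.1 lists as a seriousness criterion "Congenital anomaly/birth defect in the offspring of a subject who received avapritinib". Section 9.6 itself requires follow-up and outcome reports for all pregnancies, and rapid reporting of any SAE during pregnancy, but also states that a pregnancy without complications is neither an AE nor an SAE.

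**The concern.** The female reporting window matches the female contraception window. The partner window does not match the male one: it closes at day 30, while the male precaution runs on to day 90. The pattern suggests that the female window was applied to partners without adjustment.

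The 90 days are consistent with a finding reported in Section 5.5.2: "Hypospermatogenesis was observed in the testis and epididymis of rats and dogs and did not recover after 2-week recovery". If the protocol asks for contraception to day 90, a conception on, say, day 60 is a failure of that precaution, and the sponsor would want to know of it. Section 9.6 does not ask for it.

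What is at stake is the report that starts follow-up. Without it, nobody is required to follow the pregnancy to its outcome, and learning of an adverse outcome is left to chance. Section 10 treats safety data from this study as continuous with the patients' data from their earlier avapritinib studies, so a missed report would also be missing from that wider record.

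**Working it through.** No sample size, power or event count is involved. The check compares the stated windows and then traces a late partner pregnancy through each rule.

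**Windows after the last dose**

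| Group | Contraception required (4.4 criterion 5; 5.5.1) | Pregnancy reportable (9.6) | Difference |
|---|---|---|---|
| Female patients | 30 days | 30 days | 30 − 30 = 0 days |
| Partners of male patients | 90 days | 30 days | 90 − 30 = 60 days (days 31–90) |

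As a share of the male post-dose period: 60 / 90 = 67%. This is a share of calendar days only. It is not a share of expected pregnancies, and it leaves out the on-treatment period, which Section 9.6 covers in full.

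Matching the partner window to the stated male period would give 90 − 90 = 0 uncovered days.

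**An uncomplicated partner pregnancy conceived on day 60**

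1. Section 9.6, reporting trigger: not met, because day 60 is past day 30.
2. SAE route: not met. Section 9.6 says an uncomplicated pregnancy is neither an AE nor an SAE.
3. AESI route: not met. Section 9.3 lists cognitive effects and intracranial bleeding only.
4. Section 8 and Section 6.2.5, late events: not met. They extend past 30 days only for related SAEs (and AESIs, in Section 8).
5. Section 9.6, follow-up of all pregnancies: this comes after the 30-day definition and is most naturally read as referring to those pregnancies. A broader reading is possible but is not stated.
6. Section 9.6, duty of the male patient to notify: worded for a man taking avapritinib, so it does not clearly cover one who has stopped.
7. Table 1: no visit is scheduled after EOT, so no planned contact would bring the pregnancy to light.

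Result: no mandatory report or follow-up.

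**The same pregnancy, later found to involve a congenital anomaly**

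Section 9.1 makes the anomaly serious, with no time limit and without restriction to female subjects. Section 9.5 classes an event as related unless exposure, timing or a clear other cause rules it out. Sections 6.2.5 and 8 then make it reportable after day 30, and Section 9.2 gives the investigator 24 hours from awareness. Result: reportable if it is assessed as related and the investigator learns of it.

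**An undefined term**

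Section 9.6 does not say whether a pregnancy occurs at conception or at detection, and it includes positive tests. The 60-day and 0-day differences above count by conception. If detection is meant, a conception shortly before day 30 could also fall outside the window, in either group.

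**The case against.** The strongest reply concerns consequence. A reader might infer that a congenital anomaly after a late partner pregnancy could never reach the safety database, or that no rule at all would capture it. The documents do not support that: Sections 6.2.5, 8, 9.1, 9.2 and 9.5 together provide an SAE route, and the causality rule leans towards reporting. This part of the objection stands. What remains is that the route depends on the investigator becoming aware of the event, and nothing in the plan arranges for that.

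A reader might also infer that two-thirds of exposed partner pregnancies would be missed. The 67% is a share of days and says nothing about the number of pregnancies.

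Nor does the protocol declare men to be at risk for 90 days. It states a contraception requirement; a risk period is an inference from it, in line with Section 5.5.2 but not written down. No section says the two windows must be equal, so this is a misalignment between two rules and not a direct contradiction.

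Finally, the practical reach is small. About 5 patients of both sexes are expected (Section 4.1), GIST is most often diagnosed between ages 50 and 80 (Section 1.1.1), and Section 5.5.1 requires condoms plus a highly effective partner method to day 90. Pregnancy is not an AESI, and no summary in Section 10 uses it. All of this stands and limits the weight of the point. It does not supply the missing trigger.

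**Conclusion.** The point holds as a minor misalignment in safety reporting. As written, an uncomplicated partner pregnancy in days 31–90 after the last dose has no mandatory report or follow-up, while the protocol still requires male contraception. The uncovered span is 60 days for partners of male patients and 0 for female patients. The event is unlikely in about 5 patients, and no sample size, error rate or planned analysis is affected.

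This rests on two readings: that the 30-day limit in Section 9.6 governs which pregnancies enter its follow-up provisions, and that the 90-day contraception period marks the time over which the sponsor would want to know of a conception. If the instruction to follow all pregnancies was meant without a time limit, the remedy is only to say so.

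**What to change.** Reconcile Section 9.6 with Section 5.5.1 and exclusion criterion 5. Give partner pregnancies their own reporting window, matched to the male contraception period those sections already state, and leave the female-patient window as it is. In the same sentence, say whether the window is counted by date of conception or of detection, and make clear that a male patient's duty to notify continues to the end of that window after he stops treatment. No dose, treatment or contraception rule needs to change.

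The cost is a short amendment, which under Section 13 needs IEC approval and might call for renewed consent if it is judged to affect patients' involvement. Because Table 1 has no visit after EOT, sites would also need to give a reminder at EOT, which may itself be done by telephone, or make at most one extra contact per male patient.
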